# 7.2.4 Electrocardiograms

A 12-lead electrocardiogram (ECG) will be performed in the sitting or supine position (for at least 5 minutes).

Protocol No.: TEN-02-401

Edition No.: 1

The following ECG parameters will be recorded: heart rate, PR-interval, QRS (principal deflection in ECG)-duration, QT-interval (uncorrected), QTc-interval (corrected), RR-interval and PI's conclusion on ECG profile.

The Investigator will assess whether the ECG is normal or abnormal; abnormal will be further subdivided into clinically significant and not clinically significant. Electrocardiographic intervals and Investigator assessment of all abnormal ECGs will be recorded on the eCRF.

Additional ECGs may be obtained if clinically indicated.

# 7.2.5 Clinical Laboratory Tests

Samples must be obtained, pre-dialysis, for the clinical laboratory tests identified in Table 7-1. A coagulation profile will only be performed on patients taking warfarin.

Other evaluations and tests performed during the study, specified in the Schedule of Events (Section 1.3) will include a pregnancy test, if applicable.

# 7.2.6 Analysis of Clinical Laboratory Tests

A certified laboratory will be used to process and provide results for the clinical laboratory tests.

For any laboratory test value outside the reference range that the Investigator considers clinically significant, the Investigator will:

- Repeat the test to verify the out-of-range value.
- Follow the out-of-range value to a satisfactory clinical resolution.
- Record as an AE any laboratory test value that (1) is confirmed and the Investigator considers clinically significant, or (2) that requires a patient to be discontinued from the study, or (3) that requires a patient to receive treatment, or (4) fulfills one or more SAE criteria.

Protocol No.: TEN-02-401

Edition No.: 1

**Table 7-1: Clinical Laboratory Tests** 

Hematology a	Chemistry b	Coagulation Profile c,d	Othere
Hematocrit Hemoglobin Red blood cell (RBC) count White blood cell (WBC) count Neutrophils (%) Lymphocytes (%) Monocytes (%) Basophils (%) Eosinophils (%) Platelet count	Albumin Alanine aminotransaminase (ALT) Aspartate aminotransaminase (AST) Alkaline phosphatase Bilirubin, total Bicarbonate Blood urea nitrogen (BUN) Calcium, total Chloride Creatinine Creatine kinase Glucose Magnesium Phosphorus f Potassium Sodium	Prothrombin time Activated partial thromboplastin time	Serum pregnancy g FGF-23 ch Parathyroid Hormone (PTH) e c-reactive protein e Aldosterone e

a Whole blood.

b Serum.

c Plasma.

d Only in people treated with Warfarin.

May be performed from the biomarker samples, if desired and will not be part of the clinical study report.

Serum phosphorus is also performed separately from standard clinical laboratory tests at protocol specified time points.

Serum pregnancy tests will only be performed on women of child-bearing potential.

Intact FGF-23 will be measured.

Protocol No.: TEN-02-401

Edition No.: 1

#### 7.2.7 Adverse Events

The Investigator is responsible for ensuring that all staff involved in the study are familiar with the content of this section.

An AE is defined as any untoward medical occurrence in a patient administered a pharmaceutical product during the course of a clinical investigation. An AE can therefore be any unfavorable and unintended sign, symptom, or disease temporally associated with the use of an investigational product, whether or not thought to be related to the investigational product.

Patients will be monitored throughout the study for AEs, from the enrollment visit through the end of treatment (Visit 13). All AEs spontaneously reported by the patient or reported in response to the open question from the study personnel: "Have you had any health problems since the previous visit?", or revealed by observation will be collected and recorded in the eCRF. When collecting AEs, the recording of diagnoses is preferred (when possible) to recording a list of signs and symptoms. In instances of well-recognized symptoms, they can be recorded as the commonly used diagnosis (e.g., fever, runny nose, and cough can be recorded as "flu"). However, if a diagnosis is known, but there are other signs or symptoms that are not generally part of the diagnosis, the diagnosis and each sign or symptom should be recorded separately.

Adverse events that are identified at the last assessment Visit 13 (EOT) as specified in the protocol must be recorded on the AE eCRF with the status of the AE noted, and the AE must be followed until AE is resolved or stable. All events that are ongoing at this time will be recorded as ongoing on the eCRF. The procedures specified in Section 7.2.7.8 are to be followed for reporting SAEs.

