#### 1.3 Schedule of Events

Study Day	Base- line*	W1 ± 2 days	W2 ± 2 days	W3 ± 2 days	W4 ± 2 days	W6 ± 2 days	W8 ± 2 days	M 3 ± 2 weeks	M 4 ± 2 weeks	M 5 ± 2 weeks	M 6 ± 2 weeks	M 7 ± 2 weeks	M 8 ± 2 weeks	M 9 ± 2 weeks	M 10 ± 2 weeks	M 11 ± 2 weeks	M 12 ± 2 weeks	M 13 ± 2 weeks	M 14 ± 2 weeks	M 15 ± 2 weeks	M 16 ± 2 weeks	M 17 ± 2 weeks	M 18 EOT
Visit	V1	V2	V3	V4	V5	V6	V7	V8	T1	T2	V9	T3	T4	V10	T5	T6	V11	T7	T8	V12	Т9	T10	V13
ICF	X																						
I/E Criteria	X																						
Med History m	X																						
BW, Ht, Kt/V1	X							X			X			X			X			X			X
Physical Exam	X																						X
Vital Signs a	X							X			X			X			X			X			X
ECG	X																						X
Clin Lab Tests b	X							X			X			X			X			X			X
Pregnancy Test c	X																						X
Drug Dispense j	X	$X^{j}$	$X^{j}$	$X^{j}$	$X^{j}$	X	$X^{j}$	X			X			X			X			X			
Drug Return k		X	X	X	X	X	X	X			X			X			X			X			X
KDQoL/DSI d	X										X						X						X
s-Phosphorus e	X	X	X	X	X	X	X	X			X			X			X			X			X
FGF23	X							X			X			X			X			X			X
Exploratory Biomarkers f	X							X			X			X			X			X			X
AE Assess g	X	X	X	X	X	X	X	X	X	X	X	X	X	X	X	X	X	X	X	X	X	X	X
ConMedsh	X	X	X	X	X	X	X	X	X	X	X	X	X	X	X	X	X	X	X	X	X	X	X

- \* All baseline procedures, except informed consent and I/E criteria will come from the TEN-02-301 EOT visit; V= visit at office or dialysis center; T= telephone visit;
- W= week, weekly visits are after a short dialysis interval and have a ± window of 2 days; M= month; monthly visits have a ± window of 2 weeks.
- a If collected as part of standard of care, that data can be used and includes blood pressure and pulse.
- b Clinical laboratory tests: All blood collections are performed pre-dialysis.. See Table 7-1 for list of tests.
- c Pregnancy tests (serum) will only be performed on women of child-bearing potential.
- d KDQoL (KDQoLTM-36), Kidney Disease and Quality of Life survey. DSI, Dialysis Symptom Index survey is for English speakers only and is not validated in other languages.
- e Serum phosphorus will be measured by a central laboratory.
- f Serum and plasma samples will be collected at the same time as the clinical laboratory evaluation and sent to the central laboratory for storage.
- g AEs and SAEs will be collected from consenting to the end of study.

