#### 4 STUDY DESIGN

# 4.1 Design Summary

Patients who complete the TEN-02-301 study (PHREEDOM) at Visit 23, may be eligible to enroll into TEN-02-401 (NORMALIZE).

Patients will be required to sign an ICF and meet all inclusion and no exclusion criteria. No baseline assessments will be performed as part of this protocol; all baseline data for TEN-02-401 will be taken from the TEN-02-301 End of Treatment (EOT) visit. Patients from the

Protocol No.: TEN-02-401

Edition No.: 1

TEN-02-301 tenapanor arm will either receive only tenapanor or be given sevelamer in addition to tenapanor based on their sP following a protocol-specified dose titration schedule. Patients from the TEN-02-301 sevelamer arm will be given tenapanor in addition to their sevelamer dose and the sevelamer dose will then be adjusted based on their sP following a protocol-specified dose titration schedule. Patients will be monitored for safety and efficacy with in-office and telephone visits for up to an additional 18 months.

All study visits must be scheduled after a short dialysis interval (only for HD patients; e.g., Wednesday or Friday for patients on a MWF schedule and Thursday or Saturday for patients on a TThS schedule). Body weight and blood collections for laboratory assessments **must** be performed pre-dialysis. All other assessments may be performed pre-, during, or post-dialysis but should be performed at the same time at each visit. For patients receiving PD, visits should be performed on the same day each week, if possible.

Investigators may decrease or increase the dose of tenapanor based on sP levels and/or GI tolerability. The changes must be made in 10 mg increments to a minimum of 10 mg BID or a maximum of 30 mg BID. The dose of sevelamer carbonate may be adjusted based on the guidance provided in Section 4.1.1 or the sevelamer package insert. Investigators have flexibility to dose sevelamer, TID, BID or QD based on their experience with each patient or as per package insert.

Laboratory efficacy endpoints will be assessed at various times throughout the study; sP will be measured at every visit.

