#### 6.1.3 Dose Adjustments

All patients in the tenapanor group will start at the dose that they were receiving at the end of the TEN-02-301 study. Dosing regimens can be adjusted based on the most recent sP laboratory data (central laboratory data or standard of care local laboratory data).

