# 7.2 Data Collection Prior to Enrollment

No baseline assessments will be performed as part of this protocol; all baseline data for TEN-02-401 will be taken from the TEN-02-301 End of Treatment (EOT) visit, if available, and include the following:

- Date of birth, gender, and race
- Weight (pre-dialysis) and height (kg and cm, respectively)
- Kt/V most recent value prior to enrolling into TEN-02-401

Protocol No.: TEN-02-401

Edition No.: 1

- KDQoL survey
- DSI survey (for English speakers only)
- Medical history (major medical conditions taken from TEN-02-301)
- Physical examination
- Vital signs (pre-dialysis)
- Electrocardiogram (ECG) evaluation
- Blood sample for clinical laboratory tests
- Pregnancy test, if applicable
- Blood sample for FGF23 and exploratory biomarkers
- Concomitant medications

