#### 7.2.7.7 Serious Adverse Events

An SAE is any AE occurring from Enrollment through final study visit (V13), at any dose that results in any of the following outcomes:

- Death
- A life-threatening adverse drug experience
- Inpatient hospitalization or prolongation of existing hospitalization
- A persistent or significant disability/incapacity
- A congenital anomaly/birth defect

Protocol No.: TEN-02-401

Edition No.: 1

Important medical events that may not result in death, be life threatening, or require hospitalization may be considered an SAE when, based upon appropriate medical judgment, they may jeopardize the patient and may require medical or surgical intervention to prevent any of the outcomes listed in this definition. Examples of such medical events include allergic bronchospasm requiring intensive treatment in an emergency room or at home, blood dyscrasias or convulsions that do not result in inpatient hospitalization, or the development of drug dependency or drug abuse.

Note: SAEs require immediate reporting to

Adverse Events" below for details.

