### 8 METHODOLOGY/STUDY VISITS

### 8.1 Baseline, Visit 1

Prior to enrollment, the Investigator will inform each prospective patient of the nature of the study, explain the potential risks, and obtain written informed consent from the patient prior to performing any study-related procedures.

No baseline assessments will be performed as part of this protocol; all baseline data for TEN-02-401 will be taken from the TEN-02-301 End of Treatment (EOT) visit and will consist of the following:

- Informed consent
- Inclusion and exclusion criteria (Section 5)
- Weight (pre-dialysis)
- Kt/V (most recent measurement prior to enrolling into TEN-02-401)
- Medical history (major medical conditions taken from TEN-02-301)
- Phosphate binder used and dose
- KDQoL survey
- DSI survey (for English speakers only)
- Physical examination (Section 7.2.2)
- Vital signs (pre-dialysis) (Section 7.2.3)
- ECG evaluation (Section 7.2.4)
- Clinical laboratory tests (pre-dialysis) (Section 7.2.5)
  - Serum chemistry
  - Hematology
  - o Coagulation profile (if applicable)
- Serum pregnancy test, if applicable
- FGF-23, and exploratory biomarker sample (pre-dialysis)
- Dispense study drug

Protocol No.: TEN-02-401

Edition No.: 1

- Begin collecting adverse events
- Review concurrent medications

# 8.2 Weeks 1, 2, 3, 4, 6, and 8, Visits 2, 3, 4, 5, 6, and 7

- Serum phosphorus (pre-dialysis)
- Return/accountability of study drug
- Dispense study drug
- Adverse event reporting
- Review concurrent medications

# 8.3 Months 3, 6, 9, 12, and 15, Visits 8, 9, 10, 11, and 12

- Weight (pre-dialysis)
- Kt/V (most recent measurement prior to screening)
- KDQoL survey (not Months 9 and 15, Visits 10 and 12)
- DSI survey, for English speakers only (not Months 9 and 15, Visits 10 and 12)
- Vital signs (pre-dialysis) (Section 7.2.3)
- Clinical laboratory tests (pre-dialysis) (Section 7.2.5)
  - Serum chemistry
  - o Hematology
  - o Coagulation profile (if applicable)
- FGF-23, and exploratory biomarker sample (pre-dialysis)
- Return/accountability of study drug
- Dispense study drug
- Adverse event reporting
- Review concurrent medications

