### 9.4.7 Safety Analyses

Safety analyses include summaries for adverse events, clinical laboratory tests, vital signs, body weights, 12-lead ECGs, and physical examinations. These summaries will be provided for the Safety Analysis Set and each TEN-02-301 treatment arm (tenapanor or sevelamer).

Adverse events will be coded using the Medical Dictionary for Regulatory Activities (MedDRA). Summary tables and listings will be provided by system organ class and preferred term for treatment-emergent adverse events (TEAEs). Actual values and change from baseline values for clinical laboratory tests, vital signs, body weights, and ECGs will be descriptively summarized by visit. The number and percentage of patients in each physical examination category will be presented by visit.

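### Adverse events are counted from TEN-02-401 enrolment in both arms, so the by-arm TEAE table sets first tenapanor exposure against continued exposure in completers

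*Combined protocol and SAP*

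**What the plan says.** Four places set the start of collection. Section 7.2.7: "Patients will be monitored throughout the study for AEs, from the enrollment visit through the end of treatment (Visit 13"). Footnote g to the Schedule of Events (1.3): "AEs and SAEs will be collected from consenting to the end of study". The Visit 1 list in 8.1: "Begin collecting adverse events". Section 7.2.7.7, for serious events: "An SAE is any AE occurring from Enrollment through final study visit (V13").

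The arms enter with different tenapanor histories. Completion of TEN-02-301 is an entry criterion (5.1). Section 6.1.3 says: "All patients in the tenapanor group will start at the dose that they were receiving at the end of the TEN-02-301 study". By contrast, 4.1 says that patients from the parent study's "sevelamer arm will be given tenapanor in addition to their sevelamer dose".

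Section 9.4.7 tabulates TEAEs by system organ class and preferred term and adds: "These summaries will be provided for the Safety Analysis Set and each TEN-02-301 treatment arm (tenapanor or sevelamer"). It does not define TEAE, adjust for exposure time or split events by time since first tenapanor dose. The parent-study data listed for carry-over in 7.2 include "Medical history (major medical conditions taken from TEN-02-301") but no adverse events. Section 3.2 makes it a secondary objective to compare the long-term safety of tenapanor alone and combined with sevelamer.

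**The concern.** Sections 2.5 and 7.2.7.1 describe softer or looser and more frequent stools as an expected consequence of how tenapanor works. Events of this kind tend to cluster soon after starting. In the sevelamer arm that early period lies inside the TEN-02-401 window. In the tenapanor arm it lies in the parent study, and patients who stopped there because they could not tolerate the drug are not eligible here. The two columns of the TEAE table would then differ even if adding sevelamer changed nothing.

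Events that persist across the rollover are a second problem. A tenapanor-arm patient may enter with an unresolved event, and the plan does not say whether it is recorded, under which onset date, or whether it counts as treatment-emergent. At stake is the long-term safety objective: a reader could credit the combination with an excess that comes from starting tenapanor, or miss a persistent burden in the tenapanor arm.

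**Working it through.** The plan states no adverse event rate, so there is no figure to reproduce. The structural point comes from reading the sections together; the arithmetic only shows how large the effect could be.

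**Exposure periods.** Let D be the months a tenapanor-arm patient spent on tenapanor in TEN-02-301 (not given in the documents). Over 18 months of TEN-02-401, the sevelamer arm covers months 0 to 18 since first tenapanor dose and the tenapanor arm covers months D to D+18. They overlap only from D to 18, a span of 18 − D months. If D were 6 the overlap would be 12 months; if 12, 6 months (both assumed). Months 0 to D have no tenapanor-arm data in this study.

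**Gap with no true regimen difference.** Assumptions, none from the documents: a share q of new tenapanor starters has at least one stool-related event in the first 3 months (30-50%); the rate otherwise is h per month in both arms (1-2%); follow-up is complete to 18 months.

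- Tenapanor arm: 1 − exp(−18h)
- Sevelamer arm: 1 − (1 − q)·exp(−15h)
- Gap: exp(−18h) − (1 − q)·exp(−15h)

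| q | h per month | Tenapanor arm | Sevelamer arm | Gap (points) |
|---|---|---|---|---|
| 30% | 1% | 16.5% | 39.8% | 23.3 |
| 30% | 2% | 30.2% | 48.1% | 17.9 |
| 50% | 1% | 16.5% | 57.0% | 40.5 |
| 50% | 2% | 30.2% | 63.0% | 32.7 |

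All four combinations are needed: the extremes come from pairing a low q with a high h and the reverse. The range is about 18 to 41 points.

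**A second model.** Give both arms the same risk p of an event since first tenapanor dose, and let a share f of the tenapanor arm's events have begun in TEN-02-301. The observed rates are p in the sevelamer arm and p(1 − f) in the tenapanor arm, a gap of p·f. With p = 20-40% and f = 25-90% (assumed), the gap runs from 0.20 × 0.25 = 5 points to 0.40 × 0.90 = 36 points.

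**What could offset it.** Tenapanor-arm patients with serum phosphorus above 4.5 mg/dL have sevelamer added (4.1.1). If a further share r of that arm has an event from newly added sevelamer, the first model's gap becomes (1 − r)·exp(−18h) − (1 − q)·exp(−15h). This is zero at r = 1 − (1 − q)·exp(3h): 25.7% for q = 30%, h = 2%, and 48.5% for q = 50%, h = 1%. Smaller values of r narrow the gap without closing it.

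**Events ongoing at entry.** If 50-75% of the 150-200 patients come from the tenapanor arm (assumed), that arm has 75 to 150 patients. If 5-15% of them (assumed) enter with an ongoing event, about 4 (0.05 × 75) to 23 (0.15 × 150) patients have an event with no stated handling.

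**The case against.** The strongest reply is that restarting collection at rollover is normal in an extension study. Events that began in TEN-02-301 belong to that study's safety data, the summaries here are descriptive, and no between-arm safety test is planned. That is fair: the restart is not itself an error. The difficulty arises when columns with different exposure histories are set side by side under an objective to compare safety.

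Several stronger readings are tempting, and the documents do not support them:

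- A reader might infer that tenapanor-arm events ongoing at entry are never counted. Section 7.2.7 does not limit recording to new onsets: it takes in events volunteered, observed, or reported when asked about problems since the previous visit. A persistent event could be recorded, and a worsening one might count. The asterisk note in 1.3 could even be read as taking the baseline adverse event assessment from TEN-02-301, although footnote g and 8.1 point the other way. What stands is that TEAE is undefined and no rule covers these events.
- A reader might infer that every first-exposure event in the sevelamer arm is counted. Under 7.2.7.1 a stool change is an adverse event only if the patient finds it bothersome, in either arm.
- A reader might infer that the sevelamer arm alone starts combination therapy and must therefore look worse. Tenapanor-arm patients may also start the combination here, and the restart also leaves out the sevelamer arm's earlier events on sevelamer. The direction is likely, not certain.

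Section 9.1 also says that a separate SAP will govern. It may define TEAE, but the supplied text contains no such definition. A standard definition alone would still leave the arms mismatched on exposure.

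**Conclusion.** The point holds as a structural one. A single window starting at TEN-02-401 enrolment covers one arm starting tenapanor and one arm of completers continuing it, and the planned table separates patients only by those arms. The table cannot tell an effect of the combination from an effect of starting tenapanor. It probably overstates early stool-related events in the sevelamer arm relative to the tenapanor arm. Under the first model's rates and full follow-up, the gap with no true difference is about 18 to 41 points; the second model gives 5 to 36. These are illustrations, and first-exposure events from added sevelamer would reduce them.

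The conclusion also rests on sevelamer-arm patients having had no tenapanor in TEN-02-301, which the protocol implies but does not state. The documents do not show that any event will in fact be lost, only that handling at entry is unspecified. This is a low-cost improvement to the safety reporting and does not invalidate the safety data.

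**What to change.** 1. In 7.2.7 and 9.4.7, define TEAE, including how worsening of an existing event is treated. Carry events ongoing at the TEN-02-301 end-of-treatment visit into the TEN-02-401 data with an 'ongoing at entry' flag, and report their prevalence by arm beside the TEAEs.

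2. In 9.4.7, add exposure-adjusted TEAE rates by time since first tenapanor dose, taking the first-dose date from TEN-02-301 for the tenapanor arm. Contrast the arms only in exposure periods to which both contribute within TEN-02-401. Show the sevelamer arm's early period separately, as first-exposure data. Rebinning alone does not fill the tenapanor arm's early period. If TEN-02-301 events are used for that, include all tenapanor-treated patients of that study, or state plainly that the data come from completers only.

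3. State that the overall by-arm TEAE table does not estimate the effect of the combination versus tenapanor alone. The reasons are the difference in exposure history and the presence of patients on both regimens within the tenapanor arm.

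The cost is linking existing parent-study adverse event and dosing records, plus one more set of tables. No new patient procedure is needed and nothing in treatment changes.

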# 7.2.7.1 Adverse Events Associated with Change in Stool Form and/or Frequency

Based on tenapanor's ability to inhibit the absorption of dietary sodium, it is known to alter stool form and frequency in some patients. For a change in stool form and/or frequency to be considered an adverse event the patient must consider the bowel movements to be "bothersome."

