The theoretical adverse effects from tenapanor treatment in ESRD patients would be due to exaggerated pharmacological effects and may include electrolyte disturbances, metabolic acidosis, soft stools/diarrhea and reduced blood pressure. While a softening/loosening of the stool with an increased fluid loss via the intestine is an intended and desired effect of tenapanor in some patients, sensitive patients should be monitored for signs of dehydration in case of prolonged severe diarrhea. This study protocol includes clinical laboratory tests (including bicarbonate and electrolytes) and vital signs as well as specific discontinuation criteria related to phosphorus control to mitigate risks to study participants as well as to reduce the risk for severe hyper- or hypophosphatemia during the study and limit the period with risk for suboptimal phosphorus control. All patients will re-start their pre-study treatment with phosphate binders when their participation in the study ends. ESRD-HD patients are dialyzed three times per week and their health status is checked at each visit as part of standard of care. See the Investigator's Brochure for details on non-clinical and clinical results with tenapanor.

Patients will be informed both verbally and in writing about these aspects before taking part in any study-specific examination and the study will be conducted under conditions that ensure a high probability for the early detection of untoward events and for appropriate intervention.

In summary, the risks to the participants in this up to 18 month study are considered acceptable and the study results will be important for the development of a potential new drug, which could improve the treatment of hyperphosphatemia in this patient group.

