# 7.2.7.2 Recording Adverse Events

Adverse events are to be recorded on the AE page of the eCRF. Severity will be graded according to the following definitions:

Protocol No.: TEN-02-401

Edition No.: 1

 Mild: The patient experiences awareness of symptoms but these are easily tolerated or managed without specific treatment

- Moderate: The patient experiences discomfort enough to cause interference with usual activity, and/or the condition requires specific treatment
- Severe: The patient is incapacitated with inability to work or do usual activity, and/or the event requires significant treatment measures.

Action taken will be categorized as dose not changed, dose reduced, drug interrupted, drug withdrawn, required concomitant medication, required concomitant procedure and/or other.

Event outcome at resolution or time of last follow-up will be recorded as not recovered/not resolved, recovered/resolved with sequelae, recovering/resolving, fatal or unknown.

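### Section 7.2.7.1 makes a stool change an AE only if the patient finds it bothersome, so one that led to a dose cut, interruption or non-serious treatment can go unrecorded

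*Combined protocol and SAP*

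**What the plan says.** Section 7.2.7.1 notes that tenapanor is known to alter stools in some patients, and then sets one test for a stool change to count as an AE: "the patient must consider the bowel movements to be" bothersome.

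The surrounding text is broader. Section 7.2.7 says an AE can be "any unfavorable and unintended sign, symptom, or disease temporally associated with the use of an investigational product". It collects AEs that the patient volunteers, that come out of an open question, "or revealed by observation will be collected and recorded in the eCRF". Section 7.2.7.2 opens its Mild grade with "The patient experiences awareness of symptoms but these are easily tolerated", and lists the actions taken for an event, including dose reduction, interruption, withdrawal of drug and concomitant medication. For laboratory values, Section 7.2.6 includes among its AE triggers a value "that requires a patient to receive treatment".

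On dosing, Section 4.1 states: "Investigators may decrease or increase the dose of tenapanor based on sP levels and/or GI tolerability". On risk, Section 2.5 treats looser stools as expected from the mechanism and as wanted in some patients, but adds that "sensitive patients should be monitored for signs of dehydration in case of prolonged severe diarrhea".

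Long-term safety is a secondary objective (Section 3.2), and the AE tables are built from recorded treatment-emergent AEs (Section 9.4.7).

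**The concern.** The test is a necessary condition that rests on one subjective rating by the patient. It has no exception for a stool change that the investigator acted on or judged clinically important. A patient may put up with loose stools while the investigator cuts the dose because of them; under the rule as written, that is not an AE.

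Stool softening and GI events are the safety profile that the protocol itself names (Section 2.5). If stool changes that led to action stay out of the AE data, the long-term tables describe tolerability less completely than a reader would assume. No later analysis can recover what was not collected.

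**Working it through.** The documents give no figure to reproduce, so the check compares the recording rules.

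**Step 1: does another rule override the test?** I found none.
- The Section 7.2.7 clause on events seen by observation applies to AEs, and Section 7.2.7.1 decides whether a stool change is one.
- Section 7.2.7.7 defines an SAE as an AE with a serious outcome. Seriousness therefore does not bypass the test on a literal reading.
- No passage adds dose change, treatment or investigator judgment as a trigger for stool changes.

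**Step 2: if the patient does not call the change bothersome, where else would it appear?**

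| What happened | Record the protocol describes | Captured? |
|---|---|---|
| Tenapanor reduced or interrupted | Action-taken code on a recorded AE (7.2.7.2). Changes for GI tolerability need no linked AE (4.1, 4.1.1, 6.1.3) and can be made by telephone between visits (1.3) | No. Accountability records (6.2.2) show amounts, not reasons |
| New drug for a non-serious stool change | Concomitant medication, but a new drug is recorded only if it treats an SAE (6.4.1) | No |
| Patient leaves the study early | Reason recorded in the eCRF (5.3) | Yes |
| Dehydration or another clinical consequence | Its own AE (7.2.7) | Yes |
| Laboratory change judged clinically significant | AE under the rules of 7.2.6 | Yes |

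The Schedule of Events has no stool assessment. The Dialysis Symptom Index is collected from English speakers, but the protocol does not list its items, and a survey score would not show why a dose was changed.

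The gap is therefore the first two rows: dose reduction, interruption or non-serious treatment in a patient who stays in the study.

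**Step 3: direction and size.** Let S be the number of stool changes that led to one of those actions, and u the share of them not called bothersome.
- Recorded = S × (1 − u)
- Lost = S × u

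Since u lies between 0 and 1, the loss lies between 0 and S. The rule can remove events but never add them. The documents give neither S nor u, nor any AE rate, and Section 9.2 says that the sample size has no statistical basis. The size cannot be derived.

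**The case against.** The best defence is that some filter is sensible. Section 2.5 treats stool loosening as a wanted effect in some patients, and the wording of Section 7.2.7 refers to signs that are unfavorable and unintended. Asking whether the patient is bothered is one way to separate an intended effect from an unwanted one. That stands, and it is why the bothersome route should stay. It does not explain why a change serious enough to prompt a dose cut or treatment should be left out.

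It is also fair that most dose cuts for GI tolerability would follow a complaint, so u may be low. That limits the size of the gap but does not close it. The laboratory rule in Section 7.2.6 is only an analogy, because a laboratory value has no patient-perceived side.

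A reader might infer more than the documents support:
- **That Section 7.2.7.1 contradicts the general AE definition.** It narrows that definition for one effect and gives a reason.
- **That the Mild grade is nearly empty for stool AEs.** A patient can find stools bothersome yet tolerate them easily without specific treatment, and that event is Mild. The rule can remove some Mild events, no more.
- **That the loss differs between the two TEN-02-301 arms because tenapanor-arm patients have adapted.** Nothing in the protocol addresses habituation, so this is conjecture.
- **That the rule removes a stated share of all stool changes.** Any such figure needs assumed rates. It would also count changes with no clinical action, which the fix below would not generally recover.
- **That the eCRF has no field for a GI reason.** The eCRF is not among the documents.

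**Conclusion.** The concern holds in a limited form. As written, a stool change that led to a tenapanor dose reduction, interruption or non-serious treatment is not an AE unless the patient calls it bothersome, and the protocol describes no other record of it. Withdrawals and medical consequences remain covered.

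The direction is certain: the recorded rate of the drug's main known side effect can only be lowered. The size is unknown and may be small. The conclusion assumes that sites follow Section 7.2.7.1 literally and that the eCRF does not already collect the reason for a dose change. If it does, the reason for a dose change would be on record, but the event would still be missing from the AE tables.

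The change is worth making because it is cheap, it concerns the effect of most interest, and long-term safety is an objective.

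**What to change.** Change recording only; no dosing or management rule is affected.

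1. In Section 7.2.7.1, keep the bothersome route. Add that a change in stool form or frequency is also recorded as an AE, whatever the patient's rating, if it led to a change, interruption or stop of study drug, led to treatment, was judged clinically significant by the investigator, or met an SAE criterion.
2. If the eCRF does not already do so, record whether each tenapanor dose change was for sP or for GI tolerability, so that dosing and AE data can be checked against each other.
3. Flag which stool AEs met the bothersome test, so that a rate under the current rule can still be shown.
4. State in the safety analysis that other stool changes were not collected as AEs.

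The cost is one sentence in Section 7.2.7.1, up to two eCRF fields and one line in the safety analysis. The downside is a somewhat higher reported rate of stool AEs, and less direct comparability with TEN-02-301 if that study used the same rule. The flag in item 3 limits the second problem.
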